We will include 20-25 women with $\text{BMI} > 25 \text{ kg/m}^2$ who are exclusively breastfeeding a singleton term infant. Participants will provide a written informed consent. The assessments will be completed between 5 and 12 weeks postpartum, with the first assessment 5-9 weeks postpartum. No formal power calculation is possible for the acute study due to the exploratory nature of the research. We will continue including participants until we have complete data for all three sets of conditions for at least 20 participants. The crossover design of this study will decrease the interindividual variation in the statistical analysis. The women will serve as their own controls, which will remove any interindividual biological variance in breastmilk.

Experimental design

This will be a randomised cross-over study, in which all participants undergo three different conditions, in random order (Fig. 2):

- 1) Moderate intensity exercise; 48 min at $\sim 70\%$ of heart rate maximum
- 2) High-intensity exercise; 4 x 4 min at 90-95% of heart rate maximum
- 3) No exercise. Resting in the lab.

[figure not shown]

Fig. 2. Exercise will take place at 1000h, and breastmilk will be sampled at 0 h (immediately after exercise), + 1 h and + 4 h after exercise/no exercise. Dietary intake will be standardised on the day before and on the day of the experiment. Moderate intensity exercise (A), High intensity exercise (B) and No exercise (C) will be separated by one week and will be undertaken in random order.

Participants will walk or run on a treadmill during both exercise conditions. *Inclusion criteria:* Besteen 5+6 and 8+6 weeks postpartum at the first condition in the study, exclusively breastfeeding a term infant. *Exclusion criteria:* Known cardiovascular disease, type 1 or 2 diabetes.

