Breastmilk samples (~ 25 mL) will be collected at 4 timepoints in each condition. Samples obtained after exercise and in the control condition (no exercise) will be compared to a 'baseline' sample obtained at the first breastfeeding in the morning (06-0700 h) on the same day (Fig 2). Prior to the experimental protocol, all participants will undergo a maximal effort exercise test to establish their cardiorespiratory fitness (maximum oxygen uptake) and heart rate maximum. This test will be undertaken at a separate day, at least two days prior to the first experimental condition, and takes about 30 minutes. On the same day, we will also estimate the participants' body composition using a bioimpedance scale (InBody 720), and infant weight and length. We will estimate infant body composition using biompedance (BioScan tough i8-nano).

Standardised meals

Participants will be asked to register their last meal the day before the first day of experiment, as well as the breakfast and lunch on the first day of experiment using a food diary. They will be asked to repeat the exact same meals at standardised time-points in the two following days of experiment (Fig. 2).

Questionnaires

Participants will complete the International Physical Activity Questionnaire (IPAQ) at baseline. They will also provide information on their age, ethnicity, date of delivery, the infant's birth weight, length and head circumference, and whether they are smoking or taking medications.

Breastmilk sampling

Breastmilk will be sampled by the women themselves, using an electric breast pump provided to them (Medela Symphony, Switzerland). Participants will be given a detailed instruction sheet and a link to a video for milk collection procedures. Breastmilk will be collected at the described time-points in the experimental protocol. For each mother, breastmilk will be collected from one breast (of her own

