Acute Effects of Endurance Exercise with Moderate and High Intensity on Breast Milk Composition Among Women with Overweight/Obesity

Acronym: YT

NCT number: NCT05745922

Document date: 07. September 2025

Statistical Analysis Plan

Study design: Randomized crossover study

Aim: Determine the effect of moderate-intensity continuous training and high-intensity interval training on human milk concentrations of metabolites, lipids, cytokines, hormones and miRNAs in lactating women with overweight/obesity.

Overview:

- Up to N=30 women with $\text{BMI} > 25 \text{ kg/m}^2$
- Each participant goes through three conditions in random order (six possible sequences) and has milk sampled at four time points per condition (one pre-condition and three post-condition).
- Washout period: 1 week between conditions
- The samples are analysed for a range of outcome variables within different molecular data ('omics') categories.

Conditions:

- C1: No exercise, resting in the lab
C2: Moderate-intensity continuous training
C3: High-intensity interval training

Time points:

- T1: 7 am (pre-condition)
T2: 11 am (immediately after condition)
T3: 12 am (1-hour post-condition)
T4: 15 am (4 hours post-condition)

Pre-planned outcome groups measured in human milk:

- Targeted NMR metabolomics (GCF)
Metabolomics + lipidomics profile panels (Metabolon)
Cytokines (Olink)
Hormones (insulin, ghrelin, leptin, adiponectin, IGF-1)
miRNA (GCF)

Statistical analysis plan

For each outcome category, the primary objective is to evaluate the effect of conditions C2 and C3 on the outcome variables at time points T2, T3, and T4, using condition C1 and time point T1 as references. Outcomes measured in all participants will be analysed according to the intention-to-treat principle, whereas outcomes measured only in participants who followed the protocol perfectly will be analysed according to the per-protocol principle. The decision whether to include all samples or only those from participants who complied with the protocol will depend on the costs of including the extra (non-compliant) samples for each outcome group.

We will perform the following six analysis steps for all outcome groups:

1) Data preparation (batch adjustment, log transformation, imputation)

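### Meals are standardised before each visit, but women's own exercise, the exposure under study, is neither restricted nor recorded

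*Protocol*

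**What the plan says.** The control condition is "No exercise. Resting in the lab". The three conditions "will be separated by one week and will be undertaken in random order" (Protocol, Fig. 2 legend), and the SAP overview gives "Washout period: 1 week between conditions".

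The pre-visit rules concern food. The Fig. 2 legend states "Dietary intake will be standardised on the day before and on the day of the experiment". Under Standardised meals, women record certain meals around the first visit in a food diary, and "They will be asked to repeat the exact same meals at standardised time-points in the two following days of experiment". Under Questionnaires, IPAQ is completed at baseline only. I found no instruction about a woman's own exercise before a visit and no per-visit record of it.

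Before the first condition, "all participants will undergo a maximal effort exercise test to establish their cardiorespiratory fitness (maximum oxygen uptake) and heart rate maximum". On timing: "This test will be undertaken at a separate day, at least two days prior to the first experimental condition". No reason is given for two days here and one week between conditions.

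The SAP's main model (Eq. 1) has time, time-by-condition and a participant intercept. Baseline values are neither subtracted nor adjusted for. Carry-over is examined through sequence terms (Eq. 2), only for variables that pass the corrected threshold. The SAP provides for per-protocol analysis of some outcomes but does not define compliance in terms of prior exercise.

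**The concern.** The control visit defines the exercise effect. The plan controls food, a likely confounder, but not the exposure itself. On the readable text, a woman could train the evening before her control visit, or between the 06-07 h sample and the 10:00 session, and still comply. No rule would be broken and no record would show it.

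The conditions cannot be blinded. A habitually active woman might train around her rest visit and skip training around a laboratory exercise visit. The documents do not say that this happens, but nothing in them prevents or detects it. If it does, the control milk carries part of the effect being estimated, and both exercise contrasts are diluted.

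The maximal test raises a related, weaker question. It is an exhausting bout that may precede the first condition by as little as two days, and in some women that condition is control.

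**Working it through.** The plan states no power figure, effect size or SD, so there is no figure of its own to reproduce.

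**A. Own exercise before visits**

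Inputs, all assumed because the documents give none:
- E: the true acute effect.
- r: the share of E left at sampling after a bout of the woman's own exercise.
- pC and pE: the proportions of control and exercise visits preceded by such a bout.

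With additive residuals, the control mean rises by r·pC·E and the exercise mean by r·pE·E. The expected contrast is therefore E·[1 − r(pC − pE)], and the proportional loss is r(pC − pE).

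| r | pC − pE = 0 | 0.1 | 0.2 | 0.3 |
|---|---|---|---|---|
| 0.10 | 0% | 1% | 2% | 3% |
| 0.25 | 0% | 2.5% | 5% | 7.5% |
| 0.50 | 0% | 5% | 10% | 15% |

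Equal frequency gives no expected bias, only added noise. If own exercise were more common before exercise visits, the sign would reverse.

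The analysis does not repair this:
- In standard R coding, Eq. 1 has 12 fixed-effect columns (4 times × 3 conditions). It therefore estimates condition differences at the morning sample, where a residual from the previous day could show. The SAP does not subtract that sample, so the residual also stays in the later contrasts.
- Exercise taken after the 06-07 h sample would not appear there at all.
- Neither equation can adjust for exercise that was not recorded.

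**B. The maximal test**

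Inputs: six possible sequences (SAP overview); 20-25 women in the protocol and up to 30 in the SAP; a minimum gap of 2 days after the test and 7 days between conditions. Let d be the additive shift that the test leaves on the first visit (unknown).

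- Control comes first in 2 of 6 sequences: 20/3 = 6.7 women, 25/3 = 8.3, or 30/3 = 10.
- Each condition comes first with probability 1/3, so every condition mean shifts by d/3. The expected bias in C2−C1 and C3−C1 is d/3 − d/3 = 0.
- Within one woman the contrast shifts by +d, 0 or −d, each with probability 1/3, so the variance is 2d²/3. The mean contrast over n women has SD d·√(2/(3n)): 0.18d at n = 20, 0.16d at n = 25 and 0.15d at n = 30. This assumes simple randomisation; balanced sequences would give less.
- At n = 20, if d is 10% of the acute effect, 1.96 SD is 1.96 × 0.1826 × 10% = 3.6% of that effect. If d is 50%, it is 17.9%.

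Adding period to Eq. 1 raises the rank from 12 to 14, so Eq. 1 does not absorb a first-visit shift. Eq. 2 has rank 72 with or without period, so it does absorb one. It spends 72 fixed-effect parameters on 20-30 women and runs only for variables that have already passed.

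**The case against.** The strongest reply has four parts.

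**The control visit is supervised rest, and the test is on another day.** This stands. A reader might infer that the test puts exercise on control days. It does not. The most that can be said is that a first control visit is not assured to be free of residual effects.

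**Two days and one week do not contradict each other.** This also stands. The week is stated only between conditions, and nothing says it is the minimum after every bout. No document shows a milk effect lasting two days. The protocol's background (Human Milk Lipids) describes the 12,13-diHOME effect as transient. The intervals are unexplained, not inconsistent.

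**The dilution figure rests on assumed inputs.** Correct. A reader might go higher by supposing no own exercise before any exercise visit; for example, pC = 0.4, pE = 0 and r = 0.5 gives 20%. Nothing in the documents supports that asymmetry or those values. The direction itself is only plausible.

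**Absence is hard to prove.** The Fig. 2 drawing was not shown and part of the protocol was not readable, so an exercise instruction there cannot be excluded. The SAP also intends some judgement of compliance. This limits the claim to the readable text. It does not remove the gap, because neither the Standardised meals section nor the SAP mentions own exercise.

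**Conclusion.** The point holds for own exercise: in the readable documents it is neither restricted nor recorded around visits, in a trial where exercise is the exposure and participants know their condition. The size of any harm is unknown. Dilution is r(pC − pE), about 1-15% for assumed r of 0.10-0.50 and assumed frequency differences of 0.1-0.3. It is zero in expectation if own exercise is equally common before all visits.

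The maximal test is secondary. Under additivity and random order it causes no expected bias in either contrast, only chance imbalance with SD 0.18d at n = 20. What is missing is a reason for the two intervals.

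I would ask for the change because it is cheap and because exercise that was never recorded cannot be adjusted for later. Confidence is moderate, given the unreadable parts of the protocol.

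**What to change.** 1. In the protocol's Standardised meals section, extend the existing day-before and same-day standardisation: ask women to do no structured exercise outside the session on those days.
2. At each of the three visits, log any that occurs, with its timing, beside the food diary.
3. In the SAP, say how the log is used: as part of the per-protocol definition, or in a sensitivity analysis that omits or flags affected visits.
4. Reconcile or jointly justify the two-day minimum after the test and the one-week washout. Record days since the test, and consider a period term in Eq. 1. No particular interval is proposed here.

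The cost is a few sentences in the protocol, participant instructions and SAP, a short log entry per visit, a minor burden on participants, and some visits flagged as non-compliant. If visits are already complete, days since the test (from visit dates) and the period term can still be used, and unrecorded own exercise should be reported as a limitation.

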choice) for the entire study. The collected single full breast milk samples will be mixed and aliquoted into 10 x 1.8 mL sterile cryotubes and 1 x ~20 mL sterile vial, with the remaining milk for the mother to use. Samples will be frozen immediately after collection. Samples obtained after exercise training will be immediately transferred (on ice) to -80°C. The remaining samples (morning samples) will be frozen by the participants themselves at -20°C for up to 4 days before it will be transferred (cold chain) to the laboratory where it will be frozen at -80°C until analysis. The 10 x 1.8 mL aliquots will be used in the planned analyses, described below, whereas the additional 20 mL sample will be stored in a biobank for future analyses when additional funding and/or collaborations become available.

Breastmilk composition

Targeted NMR Metabolomics

Metabolic profiling of breastmilk will be analysed using nuclear magnetic resonance (NMR) spectroscopy using a Bruker Avance III Ultrashielded Plus 600 MHz spectrometer (Bruker Biospin GmbH, Germany) at NTNU MR Core Facility. After removal of residual lipids and proteins as previously described⁵⁴, each filtered sample (350 µL) will be mixed with 350 µL of 0.1 M phosphate buffer solution (pH 7.4) containing sodium 3-trimethylsilyl-(2,2,3,3-2-H3)-1-propionate (TSP) (final concentration 2 mM), and then 650 µL will be transferred into a 5 mm wide NMR tube. Metabolites will be assigned using Bruker AMIX software v.2.5 and Chenomx v.7.11 (Chenomx Inc., Canada), matching spectra to reference databases of metabolites. A mother's secretor status reflects her blood group antigens and determines her ability to synthesise certain HMOs, thus the secretor status for each individual will be determined by the high abundance (secretor) or near absence (non-secretor) of the HMO 2'-fucosyllactose in the respective milk samples with a cutoff of 100 nmol 2'FL/mL, as previously described.⁵⁵ Secretor status will be accounted for in the analysis by doing sub-group analyses of secretors vs. non-secretors.

Untargeted Global Metabolomics and Complex Lipid Panel Analysis

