- We will analyse both the combined and separate effects of time and time-condition interaction as fixed effects, and participant ID as a random intercept (Eq 3). The analysis will be reference coded, with C1 (No exercise) and T1 (morning) as reference points. We will not adjust for or subtract baseline values in the model.

Eq. 3: response matrix ~ time + time:condition + (1|id)

- Each variable will be scaled by the standard deviation of the baseline (morning) samples across conditions.
- We will use cluster bootstrapping with 1000 iterations to validate the findings and generate confidence intervals.

The results from the LMM and RM-ASCA+ analyses will guide follow-up analyses using additional machine learning models (PLS-DA, t-SNE).

5) Partial Least Squares Discriminant Analysis (PLS-DA)

- Supervised machine learning approach to analyse differences between the conditions. We will provide the model with a response matrix specifying the conditions, and the model will maximize separation between the conditions. The

method works well with small datasets and multiclass scenarios (here: multiple conditions).

- We will use PLS-DA for feature selection/to explore global structures in the data or find variables that are especially important for one time/condition compared to another. The LMM and RM-ASCA+ analyses will guide the selection of conditions/time points for comparison.
- We will perform cross-validation and permutation testing with 1000 repetitions.

6) T-Distributed Stochastic Neighbour Embedding (t-SNE)

- We will use t-SNE in an exploratory analysis to look for clusters of variables by preserving local relationships (pairwise similarities between data points, clusters).

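### Morning (T1) milk is stored differently from all later samples, so no change measured from T1 can be read as an exercise or time-of-day effect; the same-time contrasts with the control day are unaffected.

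*Protocol*

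**What the plan says.** The protocol's Breastmilk sampling section sets two storage routes. For the first sample of the day: "morning samples) will be frozen by the participants themselves at -20°C for up to 4 days". For the others: "Samples obtained after exercise training will be immediately transferred (on ice) to -80°C". The first sample is defined under Experimental design as the "sample obtained at the first breastfeeding in the morning (06-0700 h) on the same day".

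The same section states the protocol's comparison: "Samples obtained after exercise and in the control condition (no exercise) will be compared to a 'baseline' sample" from that morning.

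The SAP overview says each woman "has milk sampled at four time points per condition (one pre-condition and three post-condition"), and the control condition is listed as "C1: No exercise, resting in the lab". The primary objective is the effect of C2 and C3 at T2, T3 and T4, "using condition C1 and time point T1 as references". Step 3 fits Eq. 1, with time and time:condition as fixed effects and a random intercept per woman, and makes no subtraction of or adjustment for baseline. Step 4 uses the same structure for RM-ASCA+: "We will analyse both the combined and separate effects of time and time-condition interaction as fixed effects". T1 samples also supply the RM-ASCA+ scaling SD and the number of principal components that divides alpha.

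Neither document has a storage term, a record of days at -20°C, or a stability check.

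**The concern.** T1 is the only time point with its own storage route, and it is the reference for time. If several days in a home freezer alter an analyte, that alteration appears as a difference between T1 and everything after it. Three planned readings take in this difference:

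- the protocol's comparison of later samples with the same-day morning sample;
- the mixed-model time coefficients, which are differences from T1;
- the combined RM-ASCA+ effect, which contains the step from T1 to the later samples.

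A storage artefact could then be reported as a diurnal pattern or, on an exercise day, as a change after exercise. A handling shift shared by many analytes could also weigh heavily in the combined RM-ASCA+ effect. The SAP uses the mixed-model and RM-ASCA+ results to choose the comparisons for PLS-DA, so a misreading could carry forward.

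**Working it through.** The plan has no figure of its own to reproduce here: the protocol states that no power calculation was possible. The check has four steps.

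**1. Can storage be separated from time?** The time design has four columns, one per time point. A storage indicator (1 at T1, 0 at T2-T4) is identical to the T1 column. The rank is 4 without it and 4 with it, so no model fitted to these samples can separate the two.

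**2. Which Eq. 1 coefficients move?** Add a constant s to every T1 value. Since the T1 indicator equals intercept − T2 − T3 − T4, the intercept moves by s, each time coefficient moves by −s, and every time:condition coefficient moves by 0. Eq. 1 was fitted to simulated data: 20 women × 3 conditions × 4 times, with assumed SDs of 0.5 between women and 0.3 residual, and an assumed s = −0.3 log units.

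| Coefficient | No storage effect | s = −0.3 |
|---|---|---|
| T2 | 0.074 | 0.374 |
| T3 | 0.115 | 0.415 |
| T4 | 0.234 | 0.534 |
| T2:C2 | 0.159 | 0.159 |
| T2:C3 | 0.514 | 0.514 |
| T4:C3 | 0.362 | 0.362 |

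All six time:condition coefficients at T2-T4 are unchanged, whether or not the T1:condition terms are kept. Time effects within T2-T4 are also safe: T3 − T2 is 0.115 − 0.074 = 0.041 before and 0.415 − 0.374 = 0.041 after.

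**3. What if storage time varies?** Assume 0-4 days at −0.1 log units per day, unrelated to condition, with a true exercise effect of 0.2 (4,000 simulated trials, 20 women).

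| Quantity on an exercise day | Without storage: mean (SD) | With storage: mean (SD) |
|---|---|---|
| Change from T1 | 0.198 (0.095) | 0.398 (0.100) |
| Change from T1 minus control-day change | 0.195 (0.135) | 0.195 (0.142) |
| Same-time difference from control | 0.197 (0.096) | 0.197 (0.096) |

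The change from T1 gains the mean storage shift, 2 days × 0.1 = 0.2. The difference of changes stays centred and becomes slightly noisier. The same-time difference is untouched.

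**4. How often would a pure storage shift be called a time effect?** In the reference-coded Eq. 1, the time coefficient is the C1 change from T1. With n women, its SE in residual SDs is sqrt(2/n). For n = 20, the protocol's minimum with complete data, SE = sqrt(2/20) = 0.316. For a shift d, the two-sided rejection probability is approximately Φ(d/SE − z), plus a small opposite tail. Here z = 1.960 at 0.05 and 2.935 at 0.05/15; the divisor 15 is an assumption.

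| Assumed shift (residual SD) | d/SE | alpha 0.05 | alpha 0.05/15 |
|---|---|---|---|
| 0.2 | 0.632 | 10% | 1% |
| 0.5 | 1.581 | 35% | 9% |
| 1.0 | 3.162 | 89% | 59% |

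With the SAP's upper limit of 30 women, SE = sqrt(2/30) = 0.258, and a 0.5 SD shift gives about 49% and 16%.

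**The case against.** The strongest reply is that the design already answers the exercise question. Morning handling is the same on all three days, the resting day is there to absorb everything that differs between morning and midday, and the SAP does not subtract baseline. T1 also differs from T2-T4 in time of day and meals, so a raw change from T1 was never a clean exercise effect. RM-ASCA+ plans a separate interaction effect alongside the combined one. All of this stands, and step 2 confirms it.

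Two stronger readings are tempting:

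- *The exercise effect itself is confounded with storage.* The documents do not support this, because the time:condition terms at T2-T4 do not move. One route to real bias would be home freezing of the control-day T2-T4 samples: in the simulation this biased each exercise coefficient by the full 0.300 (T2:C2 from 0.159 to 0.459). The protocol names only samples taken after exercise for the direct route. However, its home-freezing sentence is limited to morning samples, and the control condition is spent in the laboratory, so the text points the other way. It should still be stated.
- *T1 storage distorts the RM-ASCA+ scaling and the significance threshold.* A uniform shift changes neither the T1 SD nor the T1 covariance. Only variation in storage days could, by an amount and in a direction that the documents do not allow one to estimate.

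The reply does not remove the narrower problem. The protocol's stated comparison is with the morning sample, and the SAP plans to evaluate time effects against T1 and the combined RM-ASCA+ effect without a caution on storage.

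**Conclusion.** The point holds as a limit on interpretation. Any within-condition change from T1, any time coefficient referenced to T1, and the combined RM-ASCA+ effect contain a storage component that cannot be removed. The same-time contrasts of C2 and C3 with C1 are not biased, on two conditions: the storage effect is additive on the analysed scale, and control-day T2-T4 samples take the direct -80°C route. Storage days that vary independently of condition add noise, not bias, to contrasts that use T1.

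The size is unknown. At an assumed 0.5 residual SD the risk of a false C1 time effect is about 35% at alpha 0.05 and 9% at 0.05/15. At 0.2 SD it is 10% and 1%, so the practical weight depends on analyte stability, which the documents do not address.

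**What to change.** In the SAP:

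- State that exercise effects are read only from C2 or C3 versus C1 at the same time point, that is, from the mixed-model time:condition terms at T2-T4 and the separate RM-ASCA+ interaction effect. This replaces the protocol's comparison with the morning baseline as evidence of change due to exercise.
- Report time effects within T2-T4 only, with T2 as reference.
- State that changes from T1 to later samples, and the combined RM-ASCA+ effect, will not be interpreted as exercise or diurnal change.

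In the protocol or study records:

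- Confirm that control-day T2-T4 samples go directly to -80°C.
- Record days at -20°C for each morning sample where possible.

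The cost is a few sentences, and the trial gives up diurnal claims against the morning sample. The randomised comparison is kept intact.

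Bringing the morning sample chilled to the 10:00 session is not a clear improvement. It would replace immediate freezing with about 3-4 hours unfrozen (from 06:00-07:00 to 10:00), and T1 would still be the only time point handled differently.
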